## 7 Research Process

The research process included: Screening and enrollment of subjects, Days -30 to -1 before the operation, Day 0, the day of operation, and one-year follow-up (Days 1-365) after the operation.

### 7.1 Screening and enrollment

#### 7.1.1 Screening of subjects

Qualified and authorized investigators or clinical study coordinators reviewed the medical records of subjects to screen subjects eligible for this study.

### **7.1.3 Enrollment of subjects**

If a subject met all the inclusion criteria and did not meet any exclusion criterion, he/she could be included in the retrospective analysis cohort. Subjects could be considered as enrolled in this study only if they met the following requirements:

- 1) A subject met all the inclusion criteria and did not meet any exclusion criterion; and
- 2) The ICF was signed (in terms of a research center that did not waive informed consent).

### **7.2 Days -30 to -1 before the operation**

The following information needed to be collected and recorded:

1. Demographic information and medical history of a subject before the operation: including patient age, gender, height, weight, preoperative diagnosis; past medical history, past surgical history, personal history; preoperative laboratory examination results: including white blood cells, red blood cell count, neutrophilic granulocyte count, hemoglobin content, platelet count, alanine aminotransferase (ALT), aspartate aminotransferase (AST), C-reactive protein, albumin, blood glucose, APTT, PT, and INR. If there were multiple laboratory tests before the operation, the latest results should be collected.
2. Concomitant medication: Only the administration of antibiotics within seven days prior to the operation was recorded.

### **7.3 Operation period (Day 0, the day of operation):**

The following information needed to be collected and recorded:

1. Operation: date of surgery, surgeon, surgical procedure, start and stop time of the operation, blood loss during the operation, medications, intraoperative complications, intraoperative shunt, and combined treatment;
2. Record of devices used during the operation: type, No. and batch No. of the cerebral ventricular shunt catheter; type, No. and batch No. of the pressure regulating valve; and type, No. and batch No. of shunt catheters at the abdominal cavity/the lumbar cistern/ the atria.

### **7.4 Postoperative follow-up period: Days 1-365**

An adverse event (except an anticipated adverse event) discovered during the review of postoperative history or hospital database (if any) should be recorded:

The date, description, concomitant therapy, and outcome of an adverse event, information related to the operation and the product, not matter the implanted part was taken out due to an adverse event, and concomitant medication and treatment should be recorded.

Additional records were required for the following special adverse events:

1. Infection: Infection site which is usually classified into intracranial, skin, and abdominal infections. For intracranial infection, date of infection, white blood cell count, red blood cell count, neutrophilic granulocyte count, hemoglobin content, alanine aminotransferase (ALT), aspartate aminotransferase (AST), C-reactive protein, blood glucose, traits and color of CSF, cell count, Pan's test results, contents of protein, sugar, and chloride in CSF, bacterial culture type, and bacterial susceptibility to rifampicin and clindamycin should be recorded. For skin infection and abdominal infection: white blood cell

count, red blood cell count, neutrophilic granulocyte count, bacterial culture type, and bacterial susceptibility to rifampicin and clindamycin should be recorded.

2. Obstruction of catheter: site, reason (judged by an investigator), and nature of obstruction should be recorded.

3. Leakage of CSF: date and position of leakage should be recorded.

4. Mechanical failure: type of mechanical failure should be recorded, including falling out, displacement, twisting, and rupture.

A patient who died within one year was still considered as a complete case. The form of SAE should be completed. And the death should be specified in this study endpoint table.

## **8 Adverse Event Reporting**

### **8.1 Adverse events**

#### **8.1.1 Adverse events**

Adverse event (AE) refers to any adverse medical event of a subject, no matter if it is related to this study or a research-related device.

During the assessment of a subject enrolled to this clinical study, an investigator should each time determine whether there was an AE and collect information, including date, severity, treatment, prognosis, and analysis of the AE, and research-related device, operation, or drug, in as detailed a way as possible.

Information of all AEs, research-related device failures, and other product issues should be as much as possible collected from existing medical records, and entered into CRFs.

#### **8.1.2 Anticipated operation-related adverse events**

Anticipated AE refers to an event that occurred after the operation during hospitalization (relative to the baseline change of a subject), which was an anticipated consequence of the operation. If an anticipated AE occurred, it would not be reported to the sponsor.

Currently, postoperative anticipated AEs known include:

- Wound pain within 48 hours followed by agitation
- Fever lower than 38.5°C within 48h
- Abdominal distension and constipation within 48h
- A small amount of wound exudation within 48h
- Mild anemia (hemoglobin > 90g/L)
- Increase in white blood cells within 48h

## **8.2 Unanticipated adverse device effect**

Unanticipated adverse device effect (UADE) refers to a serious adverse effect, a life-threatening issue, or death caused by or related to the devices, or a serious and unanticipated issue related to the rights, safety, or health of a subject and the devices. In addition, the nature, severity, or frequency of such an event was not specified in the study proposal, IFU, and clinical trial instructions.

## **8.3 Serious Adverse Events**

Serious adverse event (SAE) refers to any of the following adverse events:

- 1) Cause Death,
- 2) Serious deterioration of a subject's health, including:
  - a. A life-threatening illness or injury,
  - b. Permanent damage of the body structure or a body function,
  - c. Hospitalization or extension of the current hospital stay;
  - d. Medical or surgical intervention required to avoid a life-threatening disease or prevent permanent damage to the body structure or a body function,
- 3) Fetal distress, fetal death, congenital malformation, or birth defects.

In this retrospective study, planned hospitalization or medical intervention due to a disease existing before the operation not followed by serious deterioration of health was not regarded as a serious adverse event.

## **8.4 Duration of follow-up after an adverse event**

As this is a retrospective study, it did not intervene in subjects' normal treatment. Therefore, all adverse events were properly evaluated by an investigator based on medical requirements. And no additional follow-up would be performed.

## **8.5 Adverse event reporting**

Within one year after the shunt operation of a subject, all the adverse events (except anticipated adverse events) recorded in the medical records or hospital database (if any) should be reported. An investigator reported AEs to the sponsor via CRF.

An investigator should record the nature, severity, treatment and prognosis of an AE and determine the correlation with the devices, medication, or operation involved in this clinical study.

An investigator must report SAEs and UADEs to the sponsor (or a designated person) within 24h after their occurrence, and report them to the Ethics Committee in a timely manner. In the event of any request by the sponsor, additional information should be provided. The investigator should judge the time associated with the research product. The research center should report them to a local medical device adverse event monitoring organization. Death should be reported within 7 days, after it was known. A serious injury or an event that might result in death or a serious injury should be reported within 20 days after it was known. The sponsor would report to NMPA and/or a local medical device adverse event monitoring organization in line with the same requirements as those of the research

center. If the adverse event had existed or been reported in the previous reporting system, it would be unnecessary to report it repeatedly.

The sponsor should regularly inform all the clinical investigators of this study of all SAEs and UADEs.

### **8.5.1 Severity criteria**

The severity of an adverse event could be classified as mild, moderate, and severe according to the following criteria.

- Mild: It was transient and mild with no influence on daily life, and no special measures or treatment was required.
- Moderate: It had a slight impact on daily life. Measures or treatments were needed, if necessary.
- Severe: It had a serious impact on daily life. Special measures or treatment must be taken, and hospitalization was required, if necessary.

### **8.5.2 Determination of causal relationship**

The relevance between any adverse event and a research-related device should be judged, according to the following criteria, including unrelated, possibly unrelated, possibly related, probably related, and definitely related. If an AE was judged to be possibly related, probably related, or definitely related to a research-related device, such an AE was related to the devices.

- Unrelated: An AE was not related to the devices.
- Possibly unrelated: An adverse event was more likely to be related to other factors, such as concomitant medication or disease. Or the timing of the AE indicated that it was unlikely to be caused by a research-related device.
- Possibly related: An AE might be caused by a research-related device. Other reasons were not excluded, such as concomitant medication or disease. When the occurrence of an AE and the use of a research-related device had a reasonable time sequence, the causal relationship between the event and a research-related device could not be excluded.
- Probably related: An AE was probably caused by a research-related device. An AE and the use of a research-related device had a reasonable time sequence. For example, the causal relationship was proved after the device was taken out. There was unlikely to be another explanation, such as concomitant medication or disease.
- Definitely related: The type of an AE was identified as a side effect of a research-related device, which could not be explained by other reasons, such as concomitant medication and disease. The time of an AE strongly implied a causal relationship (e.g. reaction after the removal and re-implantation of a device).

## **9 Early Termination of the Study**

### **9.1 Reason of early termination**

Possible reasons of early termination include, but are not limited to, the following:

- Withdrawal of informed consent: (For a research center which required its subjects to sign the ICF) a subject decided to withdraw from this study. The decision must be "determined by the subject himself/herself" and recorded in the subject's research file;
- Early termination of this study: The sponsor might decide to suspend this study in advance for any reason.

## **9.2 Early termination of this study by a subject**

For a research center which required its subjects to sign the ICF, if a subject terminated this study in advance, the reason must be recorded in the source document and the file of the research center and submitted via CRF.

A subject who terminated this study in advance could not be replaced, and his/her data would be included in the results analysis, unless the subject submitted a written request to withdraw the data.

## **9.3 Early termination of this study by the sponsor**

The sponsor had the right to temporarily suspend or terminate in advance the research of a single research center, multiple research centers, or all the research centers at any time. The reasons include, but are not limited to: Security or ethical issues, inaccurate or incomplete data records, non-compliance, or unsatisfactory quantity or quality of enrollment.

If this study was terminated or suspended, the sponsor or its representative should follow applicable regulatory requirements to inform investigators/their organizations and regulatory authorities of the reason. The sponsor or investigators/their organizations should comply with applicable regulatory requirements to notify the Ethics Committees and submit the reason.

# **10 Statistical Methods**

## **10.1 Primary endpoint**

The primary endpoint of the study is:

Non-CSF infection within one year post implant.

Incidence of adverse events within one year post implant, which includes:

- Obstruction of a cerebral ventricular catheter
- programmable shunt system slipping
- Poor position of a catheter
- Intestinal perforation, abdominal and pseudocysts, umbilical fistula, pseudo-acute appendicitis, infection, and ascites caused by catheter
- Subcutaneous twist, rupture, distal obstruction, and distal retraction from the abdominal cavity
- Failure of a programmable shunt system

- Mechanical failure
- Obstruction or infection of the shunt path
- Leakage of CSF in an implanted programmable shunt system
- Excessive drainage
- Damage of intracranial or abdominal tissue
- Fibrous adhesion related to distal catheter

## 10.2 General considerations

The primary analysis will be descriptive in nature and will be based on information in the data collection form.

The extraction of the data from the medical records will be done by the investigators who care for the patients; in this way, the possible limitation of the study that is normally observed in other studies of review of clinical histories in which the information can be interpreted incorrectly is minimized.

## 10.3 Sample size

This study will provide infection free survival at 1 year for Hakim programmable shunt system and ensure 95% confidence bounds acceptable (half width < 5%). If  $N_0$  is the number of enrolled subjects, the number of infection free subjects after  $t$  years will be approximately:

$$N(t) = N_0 e^{-(r_1+r_2)t}$$

where  $r_1$  and  $r_2$  are the infection rate and the dropout rate respectively.

Following the Peto method, parameter estimation (e.g., infection free survival) in survival analysis will be performed. Defined  $S(t)$  as the survival rate at  $t$  years post operation, the Kaplan-Meier half 95% confidence width for the survival rate is given by:

$$\text{margin} = 1.96 \sqrt{[S(t)]^2[1 - S(t)]/N(t)}.$$

Based on published data, the annual infection rate of a normal shunt system is assumed to be 7.2%, then the 1-year infection free rate is 92.8%. With an enrollment of 130 patients and a dropout rate of 10%, by using the aforementioned formula, the sample size for infection free survival at one year post operation is given by:

$$N(1) = N_0 e^{-(r_1+r_2)} = 130 * e^{-(0.072+0.1)} = 109.$$

The half 95% confidence width of the survival given by:

$$\text{margin} = 1.96 \sqrt{[92.8\%]^2[1 - 92.8\%]/109} = 4.7\%.$$

The precision of 4.7% is less than 5% and is considered acceptable.

#### **10.4 Criteria of qualification/disqualification of the trial results**

This study is to collect post-marketing safety data on the Chinese population implanted Hakim programmable shunt system, according to product registration requirements. The occurrence, type, severity, frequency, of all AEs occurring during the study period, as well as the correlation between AEs and the product will be collected and presented. Hence, criteria of qualification/disqualification were not applicable.

#### **10.5 Interim analysis**

No interim analysis is planned for this study.

#### **10.6 Analysis plan**

All study data collected in this study will be presented in subject data listings. Statistical analyses will be performed using SAS 9.3 or later version. Other valid software might also be used as appropriate.

Data analysis will be carried out primarily using descriptive statistics. In general, mean, standard deviation, median, minimum and maximum will be calculated for continuous variables, and frequencies and percentages will be presented for categorical variables. If necessary, additional descriptive statistics may be calculated.

#### **Analysis population**

The primary analysis population for this study is the Per Protocol (PP) populations. The PP population will include all subjects who meet the inclusion/exclusion criteria

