### 6.2 Inclusion criteria

Subjects who met all of the following inclusion criteria would be enrolled:

1. The informed consent was exempted by the Ethics Committee of a research center. Or a subject or his/her legal representative signed the informed consent form (ICF) prior to the enrollment;
2. A subject had an indication suitable to use Hakim programmable shunt system;
3. A subject received a Hakim Shunt Programmable System at least one year ago.

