### 6.3 Exclusion criteria

Subjects who met any of the following exclusion criterion were excluded:

1. A subject didn't have an indication suitable to use the product;
2. A subject was known to be allergic to a component or ingredient of the product to be implanted, including silicone tubing and other components;
3. According to the comprehensive judgment of an investigator, a subject had an infection of the implant site, when the shunt was implanted, such as ventriculitis, meningitis, peritonitis, and local implant skin infection;
4. A subject was simultaneously implanted another shunt system different from Hakim programmable shunt system;
5. A subject had a contraindication of the shunt operation;
6. A subject had uncorrected coagulopathy or any bleeding disorder.

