#### **Subgroup analyses**

The main subgroups that will be analyzed, in addition to the total population per protocol, will be adults and children.

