## 12.5 Protocol deviation

Protocol deviation stands for the deviation of actual implementation of the study protocol from a particular part of the study protocol (e.g. non-compliance with inclusion/exclusion criteria). This study only retrospectively collected data. An exam item required in the protocol yet missing was not regarded as a protocol violation.

No matter if it was medically sound, or if a violation was made to protect a subject in an emergency, the violation should be reported to the sponsor. An investigator should follow procedures as well as reporting policies and requirements of the EC of the research center to report a violation to the EC.

Relevant regulations required an investigator's records should be accurate, complete, and up-to-date, including documentation recording the date and cause of each protocol violation.

Protocol violation could be classified into primary protocol violation and secondary protocol violation. A violation related to inclusion/exclusion criteria or informed consent (if applicable) or affecting the endpoint would be regarded as a primary protocol violation. Other violations other than primary protocol violations were secondary protocol violations.

The final confirmation of a protocol violation should be agreed by an investigator, a data analyst, and the sponsor.

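### The only analysis set is an eligibility-based per-protocol set, and a subject can be ruled ineligible after the infection outcome is on record, with no planned table to show the effect

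*Combined protocol and SAP*

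**What the plan says.** **Analysis set.** Section 10.6 (Analysis population) states: "The primary analysis population for this study is the Per Protocol (PP) populations". It continues: "The PP population will include all subjects who meet the inclusion/exclusion criteria". The subgroup paragraph works from the same set: "in addition to the total population per protocol, will be adults and children". No all-enrolled, full or safety set and no sensitivity analysis is defined.

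**Enrolment.** Section 7.1.3 sets as its first requirement: "A subject met all the inclusion criteria and did not meet any exclusion criterion; and". The second is signed consent at centres that did not waive it.

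**Later violations.** Section 12.5 gives failure to comply with the eligibility criteria as its example of a deviation, and adds: "A violation related to inclusion/exclusion criteria or informed consent (if applicable) or affecting the endpoint would be regarded as a primary protocol violation". On who decides: "The final confirmation of a protocol violation should be agreed by an investigator, a data analyst, and the sponsor". It does not say when this happens, or whether those deciding may know the outcome.

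**Outcome already on record.** Inclusion criterion 3 in section 6.2 reads: "A subject received a Hakim Shunt Programmable System at least one year ago". Under section 10.2 the treating investigators extract the data.

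**The criterion nearest the endpoint.** Exclusion 3 in section 6.3 applies if: "According to the comprehensive judgment of an investigator, a subject had an infection of the implant site, when the shunt was implanted". Its examples include ventriculitis and meningitis.

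**The concern.** Eligibility here is judged at least a year after surgery by people who can see what happened next. Most criteria are remote from the outcome, but exclusion 3 is not. It asks whether an infection was present at implantation, it rests on judgment, and it gives no objective definition and no cut-off date for the evidence. The preoperative laboratory list in section 7.2 has blood tests but no CSF results, whereas section 7.4 lists CSF findings for a postoperative intracranial infection. An infection diagnosed soon after surgery could therefore be read back, on later findings, as already present. No intent is needed; hindsight is enough.

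A subject so reclassified falls outside the per-protocol definition and so leaves both primary endpoints. If infected subjects are reclassified more often than others, the infection-free rate is biased upward. That rate is a main result of a single-arm safety study whose report, under section 10.7, supports extension of the product's registration.

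**Working it through.** **1. The plan's own figures (section 10.3).** Inputs: 130 enrolled, infection rate 7.2%, dropout 10%, infection-free rate S = 92.8%.

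- N(1) = 130 × e^−(0.072 + 0.1) = 109.46; the plan states 109.
- Half width = 1.96 × √(0.928² × 0.072 / 109) = 4.67%; the plan states 4.7%.

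Both reproduce. The sample size calculation is not in question.

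**2. When the per-protocol set can differ from those enrolled.** Section 7.1.3 requires eligibility for enrolment, and section 10.6 requires eligibility for the per-protocol set. If no ruling is reversed, the two sets are the same. If a ruling is reversed, that subject no longer meets the section 10.6 definition. Section 12.5 does not itself say that a confirmed violator is dropped; this follows from section 10.6.

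**3. Size.** The documents give no count of removals, so k is an assumption. Expected infections are 130 × 0.072 = 9.36, taken as 9. With k infected subjects removed, the crude infection-free proportion is 1 − (9 − k)/(130 − k). The half width uses the plan's Peto formula with that proportion and N(1) = 109 − k.

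| k infected removed | Infection-free | Change (points) | Peto half width |
|---|---|---|---|
| 0 | 121/130 = 93.1% | – | 4.6% |
| 1 | 121/129 = 93.8% | +0.7 | 4.4% |
| 2 | 121/128 = 94.5% | +1.5 | 4.2% |
| 3 | 121/127 = 95.3% | +2.2 | 3.9% |

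Three removals shift the estimate by 2.2/4.7, or nearly half the planned half width, and the interval narrows at the same time.

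**4. Other direction.** Removing 5 uninfected subjects instead gives 1 − 9/125 = 92.8%, a fall of 0.3 points.

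**5. Sensitivity to the infection rate.** The introduction cites 3% to 29%.

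- At 3% (4 of 130), one infected removal moves the rate by 4/130 − 3/129 = 0.75 points.
- At 29% (38 of 130), it moves the rate by 38/130 − 37/129 = 0.55 points.

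These are crude proportions that ignore censoring, not the Kaplan-Meier estimate planned in section 10.6. The plan assumes no overall adverse event rate, so no matching figure can be given for the second endpoint.

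**The case against.** The case for leaving the plan alone has several parts.

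- **The label does little.** The usual per-protocol losses are closed off. Subjects who terminate early stay in the analysis unless they ask in writing to withdraw their data (section 9.2), deaths count as complete cases (section 7.4), and a missing examination is not a violation (section 12.5). This stands. It narrows the point to eligibility reversals after enrolment.
- **Removals would be traceable.** A reader might infer that nothing in the plan would reveal a removed infection. The documents do not support that. Section 10.6 lists all collected data, section 11.3.2 requires source verification of eligibility and endpoints in every subject, and section 12.5 requires the date and cause of each violation to be recorded. What is missing is a table of the rate with and without such subjects.
- **The direction is not fixed.** A reader might infer that the rate will be inflated. That needs infected subjects to be removed disproportionately, which the documents do not show. Three removals would mean reclassifying a third of the expected infections.
- **An all-enrolled set would change nothing.** Read literally, section 7.1.3 means that an ineligible subject was never enrolled, so such a set would drop the same people. It would also miss exclusions made at screening, where the outcome is equally visible. This stands and shapes the fix.
- **Exclusion 3 is already tied to the time of implantation.** True for the condition, but not for the evidence used to judge it.
- **No decision depends on the result.** Section 10.4 sets no pass/fail criterion. This stands: no test result can change.

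**Conclusion.** The point holds as an open route to bias, not as a demonstrated bias. The sole analysis set depends on eligibility rulings that may be made or reversed after the outcome is on record, with no timing or masking rule, and one criterion borders on the infection endpoint. The effect is on the reported rate and its interval.

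At the planning assumptions, each infected subject removed raises the infection-free rate by about 0.7 points, and three raise it from 93.1% to 95.3%. Removing only uninfected subjects lowers it slightly. These sizes rest on assumed removal counts, 9 infections in 130 subjects and crude proportions. The conclusion also rests on reading section 10.6 to mean that a confirmed eligibility violator is left out. The change is worth making because the estimate is itself what the study delivers and the remedy is cheap.

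**What to change.** 1. **Primary set.** Define it as every implanted subject accepted at screening and entered in a CRF, whether or not later ruled ineligible, except where data are withdrawn by written request. Report the per-protocol set as a sensitivity analysis for both primary endpoints.
2. **Evidence for exclusion 3.** At screening and afterwards, judge it only on findings and samples obtained up to and including Day 0. Results reported later on those samples count. Record the decision before postoperative data are abstracted.
3. **Accounting.** Tabulate every implanted patient excluded at screening or removed from the per-protocol set on eligibility grounds, with the reason and, where the data may be used, infection status. Section 11.4 already asks centres to extract data on all their implanted patients.

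Cost: changes to protocol and SAP wording, the accounting table and one extra run of the endpoint tables. The downside is that a few ineligible subjects may stay in the primary set; the per-protocol sensitivity analysis shows how much they matter.
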